#### 9.1 Compliance

Compliance for HDI and PEG IFN will be analyzed by comparing the percentage of doses taken (as recorded in the diary) over the treatment period as prescribed by the physician.

Analysis of this primary endpoint is described on pages 22-23.

#### 9.2 Safety

The only adverse events that will be counted will be treatment-emergent Grade 3 and 4 AEs and treatment-emergent SAEs regardless of grade. These events are those that started after the start of that treatment period, or were present prior to the start of the treatment period but increased in severity, or changed from being not suspected to being suspected to be due to treatment.

Treatment-emergent adverse events will be summarized separately for each treatment group and by body system and preferred term. Any other information collected (eg, severity or relatedness to treatment) will be listed as appropriate.

Laboratory data will be summarized by presenting summary statistics of raw data and change from baseline values (means, medians, standard deviations, ranges) will be provided.

Data from other tests will be listed, notable values will be flagged, and any other information collected will be listed as appropriate. Any statistical tests performed to explore the data will be used only to highlight any interesting comparisons that may warrant further consideration.

#### 9.3 Sample Size Calculation

Due to the pilot study design, minimum sample size has not been calculated formally. The sample size of 100 patients is expected to generate data adequate to determine if a larger trial is warranted.

#### 9.4 Interim Analysis

There is no interim analysis planned for this study.

#### 10 Ethical Considerations

#### 10.1 Regulatory and Ethical Compliance

This clinical study was designed and shall be implemented and reported in accordance with the International Conference on Harmonization (ICH) Harmonized Tripartite Guidelines for Good Clinical Practice, with applicable local regulations (including European Directive 2001/20/EC, US Code of Federal Regulations Title 21, and Japanese Ministry of Health, Labor, and Welfare), and with the ethical principles laid down in the Declaration of Helsinki.

#### 10.2 Informed Consent Procedures

Eligible patients may only be included in the study after providing written (witnessed, where required by law or regulation), IRB/EC -approved informed consent, or, if incapable of doing so, after such consent has been provided by a legally acceptable representative of the patient. In cases where the patient's representative gives consent, the patient should be informed about the study to the extent possible given his/her understanding. If the patient is capable of doing so, he/she should indicate assent by personally signing and dating the written informed consent document or a separate assent form. Informed consent must be obtained before conducting any study-specific procedures (ie, all of the procedures described in the protocol). The process of obtaining informed consent should be documented in the patient source documents.

St. Luke's University Health Network (SLUHN) will provide to investigators in a separate document a proposed informed consent form that complies with the ICH GCP guideline and regulatory requirements and is considered appropriate for this study. Any changes to the proposed consent form suggested by the investigator must be agreed to by SLUHN before submission to the IRB/EC, and a copy of the approved version must be provided to SLUHN after IRB/EC approval.

Women of childbearing potential should be informed that taking the study medication may involve unknown risks to the fetus if pregnancy were to occur during the study and agree that in order to participate in the study they must adhere to the contraception requirement for the duration of the study. If there is any question that the patient will not reliably comply, they should not be entered in the study.

## 10.3 Responsibilities of the Investigator and IRB/EC

The protocol and the proposed informed consent form must be reviewed and approved by a properly constituted IRB/EC before study start. A signed and dated statement that the protocol and informed consent have been approved by the IRB/EC must be given to SLUHN before study initiation. Prior to study start, the investigator is required to sign a protocol signature page confirming his/her agreement to conduct the study in accordance with these documents and all of the instructions and procedures found in this protocol and to give access to all relevant data and records to SLUHN monitors, auditors, Clinical Quality Assurance representatives, designated agents of SLUHN, IRBs/ECs, and regulatory authorities as required. If an inspection of the clinical site is requested by a regulatory authority, the investigator must inform SLUHN immediately that this request has been made.

#### 10.4 Publication of Study Protocol and Results

SLUHN will ensure that the key design elements of this protocol will be posted in a publicly accessible database such as clinicaltrials.gov. In addition, upon study completion and finalization of the study report the results of this trial will be either submitted for publication and/or posted in a publicly accessible database of clinical trial results.

#### 11 Protocol Adherence

Investigators ascertain they will apply due diligence to avoid protocol deviations. All significant protocol deviations will be recorded and reported in the CRF.

#### 11.1 Protocol Amendments

Any change or addition to the protocol can only be made in a written protocol amendment that must be approved by SLUHN and the IRB/EC. Only amendments that are required for patient safety may be implemented prior to IRB/EC approval. Notwithstanding the need for approval of formal protocol amendments, the investigator is expected to take any immediate action required for the safety of any patient included in this study, even if this action represents a deviation from the protocol.

# 13 Appendices

# 13.1 Chemotherapy Convenience and Satisfaction Questionnaire (CCSQ)

Below is a list of statements that people receiving chemotherapy like yours have said are important. For each statement, please choose the reply that best fits your experience with receiving chemotherapy, and circle the number corresponding to your reply.

"Chemotherapy" means the drug(s) you receive to treat your cancer or tumor.

	Chemotherapy Experience - 1	Not at all	A little bit	Some- what	Quite a bit	Very Much
CS1	Chemotherapy treatment takes up my time .	0	1	2	3	4
CS2	My chemotherapy treatment takes up my family's time .	0	1	2	3	4
CS3	I worry about side effects from chemotherapy treatment.	0	1	2	3	4
CS4	My chemotherapy treatment causes me physical pain.	0	1	2	3	4
CS5	Receiving chemotherapy is inconvenient.	0	1	2	3	4
CS6	I worry that my chemotherapy will not be effective.	0	1	2	3	4
CS7	Chemotherapy treatment seems harmful to me.	0	1	2	3	4
CS8	My chemotherapy schedule is stressful to me .	0	1	2	3	4
CS9	My chemotherapy schedule is stressful to my family .	0	1	2	3	4
GP5	I am bothered by side effects of treatment.	0	1	2	3	4
	Please answer this last question about how you have felt this past week.					
GF7	I am content with the quality of my life right now.	0	1	2	3	4

Considering your experience with chemotherapy to date, please respond to the following questions.

	Chemotherapy Experience - 2	No, not at all	Yes, to some extent	Yes, for the most part	Yes, completely
CS 10	Are you satisfied with the current results of your chemotherapy?	0	1	2	3

		No	Maybe	Yes
CS 11	Would you recommend this chemotherapy to others with your illness?	0	1	2
CS 12	Would you choose this chemotherapy again?	0	1	2

		Poor	Fair	Good	Very Good	Excellent
CS 13	How would you rate this chemotherapy?	0	1	2	3	4

# Resource Utilization

A "cycle" of therapy with interferon is defined as one month of treatment and includes the days on which you get an infusion or injection or both, and also the days after that until you get another infusion or injection. Each month is separate cycle. If you have any question about what period of time makes up one "cycle" of treatment, your doctor or nurse can tell you.

1.	How many times did you go to the hospital or doctor's office for any reason (including scheduled visits) during the previous cycle?
	times during the previous cycle to the hospital
	times during the previous cycle to the emergency room or clinic
	times during the previous cycle to the doctor's office
2.	What was the average length of time spent on these visits, including travel to and from, waiting time, time with doctor or nurse, drug administration time, and testing/procedure time?  days during the previous cycle for an average hospital visit
	hours during the previous cycle for an average emergency room or clinic visit
	hours during the previous cycle for an average doctor's office visit
3.	How many total hours did you miss from work and/or your usual activities during your previous treatment cycle?
	hours missed during the previous cycle
4.	How many total hours have your friends or relatives missed from work and/or their usual activities because you needed their help during your previous treatment cycle?
	hours missed during the previous cycle

# 13.2 FACT-BRM (Version 4)

#### FACT-BRM (Version 4)

Below is a list of statements that other people with your illness have said are important. Please circle or mark one number per line to indicate your response as it applies to the past 7 days.

	PHYSICAL WELL-BEING	Not at all	A little bit	Some- what	Quite a bit	Very much
GP1	I have a lack of energy	0	1	2	3	4
GP2	I have nausea	0	1	2	3	4
GP3	Because of my physical condition, I have trouble meeting the needs of my family	0	1	2	3	4
GP4	I have pain	0	1	2	3	4
GP5	I am bothered by side effects of treatment	0	1	2	3	4
GP6	I feel ill	0	1	2	3	4
GP7	I am forced to spend time in bed	0	1	2	3	4
	SOCIAL/FAMILY WELL-BEING	Not at all	A little bit	Some- what	Quite a bit	Very much
GS1	I feel close to my friends	0	1	2	3	4
GS2	I get emotional support from my family	0	1	2	3	4
GS3	I get support from my friends	0	1	2	3	4
GS4	My family has accepted my illness	0	1	2	3	4
GS5	I am satisfied with family communication about my illness	0	1	2	3	4
GS6	I feel close to my partner (or the person who is my main support)	0	1	2	3	4
QI	Regardless of your current level of sexual activity, please answer the following question. If you prefer not to answer it, please mark this box and go to the next section.					
GS7	I am satisfied with my sex life	. 0	1	2	3	4

#### FACT-BRM (Version 4)

Please circle or mark one number per line to indicate your response as it applies to the past 7 days.

	EMOTIONAL WELL-BEING	Not at all	A little bit	Some- what	Quite a bit	Very much
GE1	I feel sad	. 0	1	2	3	4
GE2	I am satisfied with how I am coping with my illness	. 0	1	2	3	4
GE3	I am losing hope in the fight against my illness	. 0	1	2	3	4
GE4	I feel nervous	. 0	1	2	3	4
GE5	I worry about dying	. 0	1	2	3	4
GE6	I worry that my condition will get worse	. 0	1	2	3	4
	FUNCTIONAL WELL-BEING	Not at all	A little bit	Some- what	Quite a bit	Very much
GF1	FUNCTIONAL WELL-BEING  I am able to work (include work at home)	at all				
GF1		at all	bit	what	a bit	much
	I am able to work (include work at home)	at all 0	bit 1	what	a bit	much
GF2	I am able to work (include work at home)	0 0 0	bit 1 1	what	a bit 3	much 4 4
GF2 GF3	I am able to work (include work at home)	0 0 0 0 0	1 1 1	2 2 2	3 3 3	4 4 4
GF2 GF3 GF4	I am able to work (include work at home)	0 0 0 0 0 0 0 0	1 1 1 1	2 2 2 2	3 3 3 3	4 4 4 4

#### FACT-BRM (Version 4)

Please circle or mark one number per line to indicate your response as it applies to the past 7 days.

	ADDITIONAL CONCERNS - Physical	Not at all	A little bit	Some- what	Quite a bit	Very much
вмт6	I get tired easily	0	1	2	3	4
HI12	I feel weak all over	0	1	2	3	4
C6	I have a good appetite	0	1	2	3	4
BRM1	I have pain in my joints	0	1	2	3	4
BRM2	I am bothered by the chills	0	1	2	3	4
BRM3	I am bothered by fevers (episodes of high body temperature)	0	1	2	3	4
BRM10	I am bothered by sweating	0	1	2	3	4
	ADDITIONAL CONCERNS - Mental					
HI8	I have trouble concentrating	0	1	2	3	4
H19	I have trouble remembering things	0	1	2	3	4
BRM7	I get depressed easily	0	1	2	3	4
BRM8	I get annoyed easily	0	1	2	3	4
BRM9	I have emotional ups and downs	0	1	2	3	4
HI6	I feel motivated to do things	0	1	2	3	4

# 13.3 Interferon Preference Questionnaire

Study Patient number:	
Interferon Preference Questionnaire	
1. Did your physician discuss the option of taking standard high dose interferon vs. pegylated interferon (Sylatron TM ) with you?	Yes □ No □
If you answered "No" to question 1, there is no need to con	nplete the remainder of the
questionnaire.	
2. Plane and the Collegeise Code as in Assume City in the control of the control	
2. Please rate the following factors in terms of its importance interferon therapy:	e with regard to your choice of type of
a. Frequency of treatment (how often the treatment is	Very important □
given)	Somewhat important
	Not important
b. Toxicity (side effects) of therapy	Very important □
	Somewhat important
	Not important
c. Effectiveness of therapy in preventing or delaying	Very important □
return of melanoma	Somewhat important
	Not important
d. Convenience of the treatment schedule	Very important □
	Somewhat important
	Not important
e. Length of therapy (one year vs. longer)	Very important □
	Somewhat important
	Not important
3. Do you perceive that your physician has recommended	Yes, I followed his/her
or has a preference between the two treatment options?	recommendation
	Yes, but I chose the other treatment
	option
	My physician did not seem to have a preference □
Ni	preference
Please add any additional comments here:	

#### 13.4 ECOG Performance Scale

Grade	ECOG
0	Fully active, able to carry on all pre-disease performance without restriction.
1	Restricted in physically strenuous activity but ambulatory and able to carry out work of a light or sedentary nature (eg, light house work, office work).
2	Ambulatory and capable of all self-care but unable to carry out any work activities. Up and about more than 50% of waking hours.
3	Capable of only limited self-care, confined to bed or chair more than 50% of waking hours.
4	Completely disabled. Cannot carry on any self-care. Totally confined to bed or chair.
5	Dead

Note: As published in Am. J. Clin. Oncol.:

Data Analysis -REVISED JULY 2023

Due to the study's pilot study design, sample size was not calculated formally. For both primary and secondary outcomes, descriptive data are presented (i.e., medians and ranges for continuous data, frequencies and percentages for categorical data).

Although the original data plan called for exploratory mixed randomized-repeated measures analysis of variance (ANOVA) to be conducted for the primary and two secondary outcomes, the pattern of missing data across patients at the designated time points was too prevalent (and appeared not to be missing at random) to ensure robust ANOVA results. Therefore, we reported separate non-parametric statistical outcomes when deemed feasible (i.e., adequate and balanced subgroup sample sizes) in an attempt to obtain as much information as possible about data trends and patterns. Because we were unable to capture within-subject correlations over time, as well as the treatment group*time interaction, our results should be interpreted accordingly.

The primary outcome was compliance with HDI and PEG IFN (i.e., percentage of doses taken based on total doses required over 53 weeks, as recorded in patient diaries), with a difference of 30% between groups deemed clinically relevant. We reported frequencies and percentages per week and an overall percentage of doses taken at the end of 53 weeks, with statistical analysis of this outcome.

Secondary outcomes were as follows (with different time points reported depending on the highest outcome frequencies):

- Comparison of the convenience and satisfaction with chemotherapy for patients on standard HDI versus PEG IFN using a chemotherapy convenience and satisfaction questionnaire (CCSQ), summation of items CS1 – GP5, with a 30% between-group difference deemed clinically relevant. Time points of comparison were baseline/week 1, week 3, week 13, week 25, and week 50.
- Item GF7, which assesses contentment with current quality of life, at baseline/week 1, week 3, week 13, week 25, and week 49.
- Item CS10, which assesses satisfaction with current results of chemotherapy, at week 1, week 3, week 13, week 25, week 37, and week 45.
- Items CS11 and CS12, which measure recommendation/choice of chemotherapy regimen, at week 1, week 3, week 13, week 25, week 37, and week 45.
- Item CS13, which rates the chemotherapy regimen overall, at week 1, week 3, week 13, week 25, week 37, and week 45.
- Treatment-related side effects that may impact the patient's health-related QoL (HRQOL) using the Functional Assessment of Cancer Therapy of Biologic Response Modifier (FACT BRM), with a 30% between-group difference in scores deemed clinically relevant. Time points of comparison were baseline/week 1, week 3, week 13, week 25, and week 50.

- The frequency of Grade 3 and 4 adverse events (AEs), according to the National Cancer Institute (NCI) Common Toxicity Criteria for Adverse Events (CTCAE) for patients on standard HDI versus PEG IFN, and the frequency of severe adverse events (SAEs), regardless of grade.
- Patients' reasons for their choice of treatment with HDI versus PEG IFN at the study's conclusion, for those cases in which patients were presented with a choice of either treatment option.

All analyses were conducted using IBM SPSS Statistics for Windows, Version 25.0 (Armonk, NY: IBM Corp.), with $p < .05$ denoting statistical significance.

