#### 5.2 Method of Assigning Patients to Treatment Groups

This is an open-label, nonrandomized study. Patients will be offered HDI and/or PEG IFN and, after discussion with their treating physician, will initiate the therapy of their choice.

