#### 6.2 Interferon Preference

For situations in which the investigator offered both treatment options, patients will be queried regarding their reasons for the choice of either HDI or PEG IFN using a standardized questionnaire created for this study (see Appendix 13.3).

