#### Primary outcome

• To compare compliance with HDI and PEG IFN (percentage of doses taken as recorded in patient diaries), with a 30% between-group difference deemed clinically relevant, a mixed randomized-repeated measures analysis of variance (ANOVA) will be conducted with treatment group (HDI versus PEG IFN) as the randomized (between-group) factor and treatment period time as the repeated measures (withingroup) factor. For the repeated measures factor of time, given the different induction phases for the two regimens (i.e., approximately 4 weeks for HDI versus 8 weeks for PEG IFN), the ANOVA will capture outcomes at baseline, 2 weeks, 3 months, 6

months and 12 months, with inclusion of the latter outcome dependent on the amount of missing data.

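### Patient and physician choose the arm, yet no comparison is adjusted, and the SAP's caveat names neither treatment-choice selection nor bias from missing data

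*SAP*

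**What the plan says.** Protocol section 5.2 states: "This is an open-label, nonrandomized study". Patients start the treatment they prefer after talking with their physician. Section 3 caps either arm at 60% of patients, which controls arm size but not comparability.

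Protocol section 9 (Primary outcome) specifies a repeated-measures ANOVA "with treatment group (HDI versus PEG IFN) as the randomized (between-group) factor" and time as the other factor. The CCSQ and FACT-BRM models follow the same form. None has a covariate.

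The SAP, a July 2023 revision written in the past tense, drops the ANOVA because missing data were too prevalent ("and appeared not to be missing at random"). In its place, "we reported separate non-parametric statistical outcomes when deemed feasible (i.e., adequate and balanced subgroup sample sizes"). For the primary outcome it reports "an overall percentage of doses taken at the end of 53 weeks, with statistical analysis of this outcome". Significance is set at the 5% level. Its caveat gives one reason for care in interpretation: "we were unable to capture within-subject correlations over time, as well as the treatment group*time interaction".

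On reasons for choice, protocol section 6.2 says: "For situations in which the investigator offered both treatment options, patients will be queried regarding their reasons". The answers are only to be described.

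**The concern.** When patients and physicians pick the treatment, the arms may differ in whatever drives the choice, such as expected tolerance, distance from the clinic or attitude to side effects. Those same things plausibly affect doses taken and questionnaire scores. A two-group test without adjustment attributes any such difference to the drug. Calling group a randomized factor encourages that reading.

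Missing data raise a second issue. Rank tests relax assumptions about the shape of the distribution, but they do not address who is missing. If outcome-related loss differs between arms, late CCSQ and FACT-BRM comparisons are biased under a rank test too. If loss is similar in both arms, they are about right.

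At stake is a pilot whose stated use (protocol section 9.3) is to help decide whether a larger trial is warranted. A reader of the SAP is told to be careful, but not about either of these two problems.

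**Working it through.** **1. What is planned and what is not**

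- Adjustment: no covariate, stratification, matching or weighting appears in protocol section 9 or in the SAP. The SAP does not name the 53-week test, so that it is unadjusted is an inference from this silence.
- Baseline by arm: the SAP already compares FACT-BRM, the CCSQ sum (CS1 to GP5) and item GF7 at baseline/week 1. Demographics, medical history and ECOG PS are collected, but no by-arm presentation is planned.
- Missing data: protocol section 9 promises that missing points will be recorded and examined for patterns, but does not say by arm.
- Caveat: it omits both selection and missingness.

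There is no stated power or derived sample size to reproduce; 100 was chosen without a formal calculation.

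**2. Illustration for compliance, true effect zero**

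Inputs from the documents: over 60% of patients complete a year of HDI (protocol section 1.1), and 60/40 patients (section 3 cap, total 100). Everything else is assumed. Completion is not the same as percentage of doses taken, and the HDI figure is applied to both arms.

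Assumed distribution: 60% of patients spread evenly over 90–100% of doses, 40% evenly over 0–90%.

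- Mean = 0.6 × 95 + 0.4 × 45 = 75.
- Variance = 0.6 × (95² + 10²/12) + 0.4 × (45² + 90²/12) − 75² = 5420 + 1080 − 5625 = 875, so SD = 29.6.

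Let a driver of treatment choice differ by d SD between arms and correlate ρ with compliance on a normal scale. Then bias ≈ d × ρ × 0.87 × SD, where 0.87 is the correlation between the normal scale and this skewed percentage.

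- d = 0.25, ρ = 0.2: 0.25 × 0.2 × 0.87 × 29.6 = 1.3 points.
- d = 0.5, ρ = 0.4: 0.5 × 0.4 × 0.87 × 29.6 = 5.2 points.

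Simulation (6,000 runs per setting, two-sided Mann-Whitney at 0.05):

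| Patients | Bias, points | Rejection |
|---|---|---|
| 60/40, d = 0 | about 0 | about 5% |
| 60/40, d = 0.25–0.5 | 1.3–5.3 | 5–16% |
| 36/24, d = 0.25–0.5 | 1.1–5.3 | 5–11% |

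Harsher assumptions give more. Take a binary factor that lowers compliance by 10–30 points (base 75, residual SD 25). If it is present in 60% v 40% of the arms, the bias is 1.9–5.6 points with 6.5–18% rejection; at 70% v 30% it is 3.5–11.1 points with 12–53%.

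**3. Illustration for FACT-BRM at week 50, true effect zero**

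Assumed: between-visit correlation 0.6, and loss related to score with a logit slope of 1 per SD.

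| Retention by arm | Bias, SD | Rejection |
|---|---|---|
| 63/63% | about 0 | 4–6% |
| 70/75% | 0.02–0.05 | 4–7% |
| 60/80% | 0.13–0.16 | 6–10% |

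So the second bias depends on a difference between arms. A 0.5 SD imbalance plus a 20-point retention gap in the same direction gives about 0.3 SD and 16–28%; in opposite directions, 3–6%.

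**4. What adjustment buys**

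If the covariate correlates r with the driver, about r² of the bias is removed. Worst case above at 60/40, linear model, unadjusted bias 4.81 points and 11.9% rejection:

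| r | Bias left | Removed | Rejection |
|---|---|---|---|
| 0.3 | 4.38 | 1 − 4.38/4.81 = 9% | 9.8% |
| 0.6 | 3.05 | 37% | 7.5% |
| 0.9 | 0.86 | 82% | 4.9% |

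Interval width with three covariates, at r = 0.3: 24.9/24.2 = 1.03 at 60/40 and 33.2/31.6 = 1.05 at 36/24.

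**The case against.** The strongest reply is that the study says what it is. The protocol labels it observational and a pilot, and calls its inference exploratory in both the Synopsis and section 9. Section 5.2 states plainly that it is not randomized, and the factor wrongly called randomized belongs to a model since withdrawn. The benchmark is a 30% difference, and the illustrated bias is far smaller. The covariates at hand may be only weakly related to treatment choice, in which case adjustment changes little. Much of this stands. It limits the weight of the point and is why the tables and the caveat matter more than any model. But an exploratory label does not tell a reader that the arms may differ at entry or in retention, and the SAP still applies a 5% significance rule.

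Three stronger readings are tempting and not supported:

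- A reader might infer that the SAP is silent on missingness. It is not: it discloses the suspicion in the same paragraph as the caveat. What is lacking is the link to the comparisons it then reports.
- A reader might infer that no baseline comparison by arm exists. The questionnaires are compared by arm at baseline/week 1; the gap is in demographics, medical history and ECOG PS.
- A reader might infer that bias could produce a difference of the size called relevant. None of the illustrated compliance settings comes near 30 points.

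**Conclusion.** The point holds as a gap in analysis and disclosure. Treatment is chosen, no comparison is described as adjusted, and the caveat omits selection and does not extend the disclosed missingness to the results.

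The size and direction of bias in this trial cannot be known from the documents. Under the main assumptions it is about 1 to 5 points of compliance, with false-positive rates up to about 16% instead of 5%; the harshest setting tried gave 11 points and 53%. These figures rest almost wholly on assumed inputs. Missingness adds bias to late questionnaire comparisons only if outcome-related loss differs by arm. The risk is therefore to claims of significance and to small differences, not to a finding near the 30% threshold. Change is worthwhile because it is cheap; confidence is medium.

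**What to change.** 1. Keep the unadjusted compliance result. Beside it, add a regression of per-patient compliance on group, adjusted for age and baseline FACT-BRM, with a robust (HC3) 95% interval. Label it post hoc and exploratory. HC3 is preferred because at 36/24 patients with no true effect it rejected 4.3% of the time, against 7.5% for a percentile bootstrap. Include ECOG PS only if it is recorded for nearly all patients, and report how many are lost, since protocol section 6 makes only the quality-of-life assessments mandatory. State that covariates weakly related to treatment choice remove little bias and that unmeasured selection remains. The Interferon Preference Questionnaire items, among patients offered both options, are an optional sensitivity analysis.
2. Tabulate demographics, medical history and ECOG PS by arm, and diary and questionnaire completion by arm and time point.
3. Extend the SAP caveat to name selection by treatment choice and, if outcome-related loss differs by arm, missingness bias in late questionnaire comparisons. Stop describing the group factor as randomized.

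A mixed model for FACT-BRM is optional only. It must state that it assumes data missing at random, which the SAP itself doubts.

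Cost: modest extra analysis on data already collected, a compliance interval about 3 to 5% wider, and residual confounding.

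A separate matter is that protocol section 5.4.1 ends all study procedures at permanent discontinuation, while the Synopsis and section 3 describe an end-of-study assessment within 21 days after it. Those passages must be reconciled.
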